Mild Liver Disease	571.2x, 571.4x, 571.5x, 571.6x	K70.2, K70.3x, K73.x, K74.xx, K75.4
Diabetes (mild to moderate)	250.0x, 250.1x, 250.2x, 250.3x, 250.7x	E10.1x, E10.5x, E10.641, E11.0x, E11.5x, E11.641, E13.0x, E13.1x, E13.5x, E13.641, E13.9
Diabetes with Complications	250.4x, 250.5x, 250.6x	E10.3xxx, E10.4x, E10.610, E11.2x, E11.3xxx, E11.4x, E11.610, E13.2x, E13.3xxx, E13.4x, E13.610
Hemiplegia or Paraplegia	342.x, 344.1x	G81.xx, G82.2x
Renal Disease	582.x, 585.x, 586.x, 588.x	N03.x, N18.x, N19, N25.xx, N27.x
Malignancy	140.x-172.x, 174.x-195.x, 201.x, 203.x, 205.x-208.x	C00.x-C43.xx, C45.x-C49.xx, C50.xxx-C76.xx, C81.xx, C88.2, C88.3, C88.8, C88.9, C90.xx, C92.xx-C95.xx, D03.xx, D45
Moderate or Severe Liver Disease	572.2x-582.8x, 456.0x, 456.1x, 456.2x	I85.xx, K72.1x, K72.9x, K75.0, K75.1, K75.2, K75.3, K75.8x, K75.9, K76.1, K76.3-K76.9, K77, K80.xx-K90.49, K90.89, K90.9, K91.2, K91.5, K92.0, K92.1, K92.2, N00.0-N03.8, N04.0-N04.9
Metastatic Solid Tumor	196.x-199.x	C77.x-C79.x, C80.x
AIDS	042.x-044.x	B20
Chronic Obstructive Pulmonary Disease and allied conditions	490.x	J40
	491.x	J41.1, J41.8, J44.x, J42
	492.x	J43.x
	493.x	J45.xxx, J44.x
	494.x	J47.x

	495.x	J67.x
	496.x	J44.9

2. If a patient had both the milder and more severe form of the condition, only count the more severe form of the condition -- Diabetes (mild to moderate) / Diabetes with complications; Mild liver disease / Moderate or severe liver disease; Malignancy / Metastatic solid tumor.
3. Weight each of the baseline conditions by the given weights and sum the number of conditions the patient has at baseline. This sum is the patient's CCI at baseline.

Table 5. CHADS₂ Stroke Risk Score

CHADS ₂ Risk Criteria		
Congestive Heart Failure	428.x	I50.xx
Hypertension	401.x-405.x, 437.2	I10-I16.x, I67.4
Diabetes	250.x	E10.xxxx, E11.xxxx, E13.xxxx
Stroke/ transient ischemic attack (TIA)	433.x1, 434.x1, 435.x, 436, 437.1x, 437.9x, 438.x	G45.0-G45.2, G45.8-G46.2, I63.xxx, I67.8xx, I67.9, I69.xxx

After assessing the risk factors and adding up the risk score, the stroke risk classifications are as below:

Score	CHADS ₂ Stroke Risk Classification
0	Low
1	Intermediate
2-6	High

Table 6. CHA₂DS₂-VASc Stroke Risk Score

CHA ₂ DS ₂ -VASc Criteria		
Congestive heart	428.x,	I50.xx,

failure or left ventricle dysfunction	398.91, 402.01, 402.11, 402.91, 404.01, 404.11, 404.91, 404.03, 404.13, 404.93, 425.4, 425.5, 425.7	I09.81, I11.0, I13.0, I13.2, I42.5, I42.6, I42.8, I42.9, I43

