Hypertension	401.x-405.x, 437.2	I10-I16.x, I67.4
Diabetes Mellitus	250.x	E10.xxxx, E11.xxxx, E13.xxxx
Stroke/TIA	433.x1, 434.x1, 435.x, 436, 437.1x, 437.9x, 438.x	G45.0-G45.2, G45.8-G46.2, I63.xxx, I67.8xx, I67.9, I69.xxx
Vascular disease (prior myocardial infarction, peripheral artery disease, or aortic plaque)	410.xx, 412.xx; 440.2x, 443.8x, 443.9x; ICD-9 proc code: 88.48; CPT code: 75710, 75716, 93922, 93923	I21.xx, I22.xx, I25.2, I70.2xx, I73.8x, I73.9, I79.1, I79.8; ICD-10 proc code: B40F0ZZ, B40F1ZZ, B40FYZZ, B40G0ZZ, B40G1ZZ, B40GYZZ, B40J0ZZ, B40J1ZZ, B40JYZZ, B41F0ZZ, B41F1ZZ, B41FYZZ, B41G0ZZ, B41G1ZZ, B41GYZZ, B41J0ZZ, B41J1ZZ, B41JYZZ

After assessing the risk factors and adding up the risk score, the stroke risk classifications are as below:

Score	CHA ₂ DS ₂ -VASc Stroke Risk Classification
0	Low
1	Intermediate
2 or greater	High

Table 7. HAS-BLED Bleed Risk Score

HAS-BLED Criteria		
Hypertension	401.x-405.x	I10-I16.x
	Drugs used to treat hypertension (GPI codes 3300, 3400, 3610, 3615, 3620, 3625, 3630, 3640, 3660, 3720, 3760)	
Abnormal renal and liver function	Renal: 580.xx-586.xx, V56.0, V56.8; ICD-9 procedure codes 39.95, 54.98; CPT codes 90935-90993, 99512, 99559	N00.0-N08, N17.0-N19, Z49.31, Z49.32; ICD-10 procedure code: 3E1M39Z, 5A1D00Z, 5A1D60Z

(1 point for each)	Liver: 070.x, 155.0x, 155.1x, 155.2x, 571.x, 572.x, 573.x, 576.8, 456.0x, 456.1x, 456.2x; ICD-9 procedure codes 39.1x, 42.91	B15.x-B19.xx, C22.x, I85.xx, K70.xx, K71.xx, K72.01-K76.1, K76.3-K77, K83.5; ICD10 procedure code: 0610xxx, 0611xxx, 0612xxx, 0614xxx, 0615xxx, 0616xxx, 0617xxx, 0618xxx, 0619xxx, 061Bxxx, 061Jxxx, 06L30CZ, 06L30DZ, 06L30ZZ, 06L33CZ, 06L33DZ, 06L33ZZ, 06L34CZ, 06L34DZ, 06L34ZZ
Stroke	433.xx-437.xx	G45.x, G46.x, I63.xxx-I66.9, I67.1, I67.2, I67.4-I67.82, I67.84x-I68.8

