Bleeding (includes anemia and other prior hemorrhage)	285.0x, 285.1x, 285.9x, 423.0x, 430.x-432.x, 455.2x, 455.5x, 455.8x, 459.0x, 531.0x, 531.2x, 531.4x, 531.6x, 532.0x, 532.2x, 532.4x, 532.6x, 533.0x, 533.2x, 533.4x, 533.6x, 534.0x, 534.2x, 534.4x, 534.6x, 562.02, 562.03, 562.12, 562.13, 568.81, 569.3, 569.83, 569.85, 569.86, 578.0, 578.1, 578.9, 599.7x, 719.1x, 784.7x, 786.3x; ICD-9 procedure code 44.43; CPT code 43255	D62, D64.0, D64.1, D64.2, D64.3, D64.9, I31.2, I60.xx, I61.x, I62.xx, K25.0, K25.2, K25.4, K25.6, K26.0, K26.2, K26.4, K26.6, K27.0, K27.2, K27.4, K27.6, K28.0, K28.2, K28.4, K28.6, K55.21, K57.11, K57.13, K57.31, K57.33, K62.5, K63.1, K63.81, K64.4, K64.8, K66.1, K92.0, K92.1, K92.2, M25.0xx, R04.0, R04.2, R04.81, R04.89, R04.9, R31.0, R31.1, R31.21, R31.29, R31.9, R58; ICD-10 procedure code: 0W3P8ZZ
Labile INRs		
Elderly (Age >65 years)	-	
Drug or alcohol abuse (1 point for each)	Drug: NSAIDs (GPI codes 6410, 6610), Anti-platelets (8515), Other aspirin-containing products (3940990215, 4399100222, 4399100223, 4399100232, 4399100405, 4399400321, 4399400456, 4399590415, 4399590419, 6030990225, 6499000220, 6499000221, 6499000225, 6499000226, 6499000232, 6499000320, 6499000321, 6499000335, 6499000340, 6499000450, 6499000460, 6499100220, 6499100222, 6499100228, 6499100330, 6499100335, 6599000222, 6599100210, 6599100220, 6599100325, 6599100430, 6599100510, 6599170220, 6599400220, 7599000210, 7599000240, 7599000310, 7599000320, 8515990220, 9990000000)	

	Alcohol: 291.xx, 303.xx, 305.0x, 357.5x, 425.5x, 571.1x, 571.2x, 571.3x; ICD-9 procedure codes 94.61-94.63, 94.67-94.69	F10.xxx, G62.1, I42.6, K70.xx; ICD-10 procedure code: HZ2ZZZZ, HZ30ZZZ, HZ31ZZZ, HZ32ZZZ, HZ33ZZZ, HZ34ZZZ, HZ35ZZZ, HZ36ZZZ, HZ37ZZZ, HZ38ZZZ, HZ39ZZZ, HZ3BZZZ, HZ40ZZZ, HZ41ZZZ, HZ42ZZZ, HZ43ZZZ, HZ44ZZZ, HZ45ZZZ, HZ46ZZZ, HZ47ZZZ, HZ48ZZZ, HZ49ZZZ, HZ4BZZZ, HZ50ZZZ, HZ51ZZZ, HZ52ZZZ, HZ53ZZZ, HZ54ZZZ, HZ55ZZZ, HZ56ZZZ, HZ57ZZZ, HZ58ZZZ, HZ59ZZZ, HZ5BZZZ, HZ5CZZZ, HZ5DZZZ, HZ63ZZZ, HZ83ZZZ, HZ86ZZZ, HZ88ZZZ, HZ89ZZZ, HZ93ZZZ, HZ96ZZZ, HZ98ZZZ, HZ99ZZZ
--	---	---

*the maximum score will be 8 since we do not have data available for labile INRs

After assessing the risk factors and adding up the score, the bleed risk classifications are as follows:

Score	HAS-BLED Bleed Risk Classification
0-1	Low
2	Intermediate
3 or greater	High

Table 8. Atrial Fibrillation Medications

Rate control medications	GPI codes starting with:	GPI 10
Beta blockers	3300	3310004510, 3310004512

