	534.6x	(with hemorrhage and perforation with/without obstruction)	K28.6

	578.0	(hematemesis)	K92.0
	ICD-9 Procedure Code 44.43	(endoscopic control of gastric or duodenal bleeding)	
	CPT code 43255	(upper gastrointestinal endoscopy including esophagus, stomach, and either the duodenum and/or jejunum as appropriate with control of bleeding, any method)	
Major lower GI bleeding (Primary Only)	562.02	Diverticulosis of small intestine with hemorrhage	K55.21
	562.03	Diverticulitis of small intestine with hemorrhage	K57.11
	562.12	Diverticulosis of colon with hemorrhage	K57.13
	562.13	Diverticulitis of colon with hemorrhage	K57.31
	569.3x	Hemorrhage of rectum and anus	K57.32
	569.85	Angiodysplasia of intestine with hemorrhage	K62.5
	578.1x	Blood in stool	K92.1
	578.9	Hemorrhage of GI tract, unspecified	K92.2
Major urogenital bleed (Primary Only)	599.7	Hematuria	R31.0 - R31.29
	626.2x and (280.0, 285.1 or 285.9)	Excessive/frequent menstruation and secondary diagnosis indicating acute bleeding (anemia)	N92.0 and (D50.0, D62, D64.9)
Other major bleeds (Primary Only)	719.1x	Hemathrosis	D62
	423.0x	Hemopericardium	I31.2
	786.3x	Hemoptysis	M25.0xx
	784.7x	Epistaxis	R04.0
	459.0x	Hemorrhage not specified	R04.2
	285.1x	Acute posthemorrhagic anemia	R04.8x, R04.9, R58
TIA (Primary Only)	435.x	Transient cerebral ischemia as the principal (primary) discharge diagnosis	G45.0, G45.1, G45.8, G45.9, G46.0, G46.1, G46.2
[REDACTED]	[REDACTED]	[REDACTED]	[REDACTED]
[REDACTED]		[REDACTED]	
[REDACTED]	[REDACTED]	[REDACTED]	[REDACTED]
[REDACTED]	[REDACTED]	[REDACTED]	[REDACTED]

APPENDIX B: Inclusion and exclusion diagnosis, procedure and CPT codes**Table 1. List of codes for atrial fibrillation**

Study Inclusion DX	ICD9 Diagnosis Codes	ICD10 Diagnosis Codes
Atrial Fibrillation	427.31	I48.0, I48.1, I48.2, I48.91

Table 2. List of codes and descriptions to identify patients with exclusion diagnoses

Study Exclusion DX	ICD9 Diagnosis Codes	ICD10 Diagnosis Codes
Hyperthyroidism	242.x	E05.00, E05.01, E05.10, E05.11, E05.20, E05.21, E05.30, E05.31, E05.40, E05.41, E05.80, E05.81, E05.90, E05.91
Orthopedic Procedures (See also procedure codes)	V43.64, V43.65	Z9664x, Z9665x
DVT	451.xx, 453.xx	I80.xxx, I82.xxx
PE	415.1x	I26.01, I26.09, I26.90, I26.92, I26.99, I27.82
Pericarditis	391.x, 393, 420.x, 423.2, 036.41, 074.21, 093.81, 098.83	A39.53, B33.23, I01.0, I09.2, I30.0, I30.1, I30.8, I30.9, I31.0, I32, M32.12

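### The Charlson liver row, the stroke-score age rule and the peptic ulcer codes are wrong as written, and all three feed the baseline tables and the propensity score candidates

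*Combined protocol and SAP*

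**What the plan says.** **Charlson liver row.** Appendix A, Table 4 gives the ICD-9 codes for moderate or severe liver disease as "572.2x-582.8x, 456.0x, 456.1x, 456.2x". The ICD-10 list for the same row ends "K92.0, K92.1, K92.2, N00.0-N03.8, N04.0-N04.9". The Renal Disease row of the same table is "582.x, 585.x, 586.x, 588.x". Step 2 of the algorithm keeps only the more severe form of paired conditions, including "Mild liver disease / Moderate or severe liver disease; Malignancy / Metastatic solid tumor".

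**The plan's other labels for these codes.** Table 7 (HAS-BLED) lists "Renal: 580.xx-586.xx, V56.0, V56.8". Its liver criterion includes "571.x, 572.x, 573.x, 576.8, 456.0x, 456.1x, 456.2x", and its bleeding criterion includes "569.85, 569.86, 578.0, 578.1, 578.9, 599.7x". Table 9 describes 578.9 as "Hemorrhage of GI tract, unspecified".

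**Stroke scores.** Section 9.3.3 awards the older-age points only above 75 in both scores, and one CHA2DS2-VASc point for 65 to 74. Section 2 (List of Abbreviations) defines both scores with age 75 or over.

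**Peptic ulcer.** Section 9.3.3 lists peptic ulcer, bleeding or not, and GERD as separate covariates and refers to Appendix A, Table 2. Table 2 has a single combined row. Its only ulcer codes are 533.xx and K27.x.

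**Use.** Sections 4 and 9.7 name the Charlson index, the stroke scores and the baseline comorbidities as candidates for the propensity score. Section 9.7 shows baseline characteristics before and after matching and adjusts for those left unbalanced.

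**The concern.** In each case the plan contradicts itself, so no outside coding reference is needed to see the fault. A programmer who follows the text would count some prior GI bleeds and some kidney disease as advanced liver disease, give 75-year-olds no age points, and miss most peptic ulcer codes.

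These variables can enter the propensity model, the balance check and the choice of covariates for further adjustment. Major bleeding is a primary outcome, so prior GI bleeding and ulcer history matter as confounders. A match can look balanced on a misdefined score and remain unbalanced on the characteristic the score was meant to measure.

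**Working it through.** **1. Charlson liver row**

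- The range 572.2 to 582.8 touches 572, 573, 574, 575, 576, 577, 578, 579, 580, 581 and 582: 11 categories.
- The plan's liver lists (Table 2: 570 to 573; Table 7: 571, 572, 573 and 576.8) share with it only 572, 573 and the single code 576.8.
- Four categories carry another label in the plan: 578 is bleeding (Tables 7 and 9), and 580, 581 and 582 are renal (Tables 2 and 7).
- The ICD-10 column independently contains K92.0 to K92.2 (GI bleeding in Table 9) and N00 to N04 (renal in Tables 2 and 7). A slip in one column, or a fault in text extraction, is therefore an unlikely explanation.
- Codes 582.0 to 582.8 and N03.0 to N03.8 sit in both the liver row and the Charlson renal row, so one diagnosis scores twice.
- Under step 2, a patient with mild liver disease and a 578.x or K92.0 to K92.2 claim moves to the severe row.
- Extent: Table 9 has 17 upper GI entries (16 ulcer codes plus 578.0) and 8 lower GI entries (562.02, 562.03, 562.12, 562.13, 569.3x, 569.85, 578.1x, 578.9), 25 ICD-9 diagnosis entries in all. Three (578.0, 578.1x, 578.9) fall in the liver range. Ulcer, diverticular and rectal bleeding codes lie outside it.

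**2. Age 75, in completed years**

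| Age | CHADS2, section 9.3.3 | CHADS2, section 2 | CHA2DS2-VASc, section 9.3.3 | CHA2DS2-VASc, section 2 |
|---|---|---|---|---|
| 74 | 0 | 0 | 1 | 1 |
| 75 | 0 | 1 | 0 | 2 |
| 76 | 1 | 1 | 2 | 2 |

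CHA2DS2-VASc age points run 1, 0, 2 across ages 74, 75 and 76. By the classes in Tables 5 and 6, a man of 75 with no other risk factor is low risk on both scores. Under the section 2 definitions he is intermediate on CHADS2 (1 point) and high on CHA2DS2-VASc (2 points). Tables 5 and 6, in the text available, have no age row to settle it.

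The share aged 75 is not in the documents. An even age spread is assumed: over 55 to 94 it is 1/40 = 2.5%, over 65 to 84 it is 1/20 = 5%, and over 70 to 79 it is 1/10 = 10%. Applied to the feasibility counts in section 4:

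- Rivaroxaban comparison: 16,604 + 25,215 = 41,819, giving about 1,045, 2,091 and 4,182 patients.
- Apixaban comparison: 6,050 + 20,930 = 26,980, giving about 675, 1,349 and 2,698 patients.

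These counts are before further exclusions and matching.

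**3. Peptic ulcer**

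- Table 4 treats 531 to 534 and K25 to K28 as peptic ulcer. Table 2 holds one of those four categories, 533/K27, which Table 9 describes as ulcer of unspecified site.
- Table 9 has 4 categories × 4 subcodes (.0, .2, .4, .6) = 16 ulcer-bleed entries. Table 2 covers the 4 under 533 and misses 12, so 12/16 = 75%.
- The merged row also includes 536.8/K30, which the same table labels dyspepsia.

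**Minor, for reconciliation**

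- The Charlson ulcer row lists 531.9x, 532.9x and 534.9x but not 533.9x, although its ICD-10 range has no gap.
- The Charlson mild-to-moderate diabetes row has E13.9 but not E10.9 or E11.9, while Tables 2 and 5 take all of E10, E11 and E13.
- Newly versus previously diagnosed AF is not tied to the first AF diagnosis, so a patient with claims on both sides of three months fits both classes. It is not a listed propensity variable.

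**The case against.** The strongest reply is that no effect on a primary estimate has been shown. Section 9.7 leaves the final covariate list open and may use only one stroke score. Age is also a separate candidate, and section 9.3.3 makes it continuous. Liver disease, renal disease and diabetes are separate items. The Charlson ulcer row and HAS-BLED bleeding capture part of what is lost. Section 4 adds empirically chosen diagnoses and procedures, and covariates left unbalanced are adjusted for. All of this limits the damage, and it stands. It does not make the definitions right.

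The age point depends on completed years. If age carried fractions, the CHADS2 fault would shrink to an age of exactly 75.0, and the CHA2DS2-VASc gap would move to ages above 74 up to and including 75. The 65 to 74 band implies completed years, and CHA2DS2-VASc has a gap on either reading.

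The size figures also have limits. The counts of patients aged 75 mainly reflect the assumed age spread. The ratios 3 of 25 and 12 of 16 count code entries, not patients. Table 4 refers to weights but prints none in the text available, so the change in Charlson points cannot be computed.

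**Conclusion.** All three definitions are wrong as written, on the plan's own labels. The certain consequence of literal programming is misclassified Charlson and stroke scores, a misclassified ulcer covariate, and wrong baseline tables before and after matching. If these candidates enter the propensity model, matching and the balance check use the wrong versions.

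Residual confounding cannot be quantified, because the documents give no prevalence by treatment arm. The age finding assumes completed years, and its patient counts also rest on the assumed 2.5% to 10% share. The liver and ulcer findings need no assumption. The definitions should be corrected, but nothing here shows that a primary result would change.

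**What to change.** 1. **Charlson liver row.** Restrict it to liver codes. Remove at least 578.x, 580 to 582, K92.0 to K92.2 and N00 to N04. Reconcile the rest of the range (574 to 577, 579, K80 to K91) with the plan's liver lists in Tables 2 and 7, which include 573.x, 576.8 and K83.5.
2. **Stroke scores.** Use age 75 or over, in completed years, in both scores, as section 2 does. State the age rule in Tables 5 and 6.
3. **Peptic ulcer.** Define it as 531 to 534 and K25 to K28, as its own covariate apart from GERD and dyspepsia.
4. **Minor.** Reconcile 533.9x and the E10/E11/E13 codes across tables. Classify AF as newly or previously diagnosed from the first AF diagnosis in the look-back, as the time-to-index-exposure covariate already does.

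These are code-list and wording edits that need no new data, and they cost least before the propensity model is fitted. Section 6 plans data analysis from 05 December 2016 and the protocol is dated 15 December 2016. If models already exist, the covariates must be re-derived and the matching repeated.

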 - Other antihypertensives (i.e., angiotensin-converting-enzyme (ACE) inhibitors, combinations)

- Antihyperlipidemics
- Corticosteroids
- Antidiabetics
- Antiarrhythmics (Amiodarone HCl, Propafenone and Flecainide, Dronedarone, Betapace (Sotalol), Tikosyn, Disopyramide (Norpace), Quinidine)
- Ketoconazole
- Antiplatelets (e.g., dypidamole, aspirin, etc.)
- NSAIDs
- **Prescribing provider specialty of NOAC treatment on index date:** The prescribing specialties will include cardiology, pulmonary medicine, hematology, internal medicine, family/general practice, geriatrics, surgery (all types, including vascular surgery), gastroenterology, neurology, emergency medicine, other physician types, other non-physician specialty, unknown.
- **Baseline Charlson comorbidity index (CCI) score:** Baseline CCI measures specific individual comorbidities that are associated with mortality that are observed in the pre-index period. A score will be calculated based on CCI criteria. (See [Appendix A, Table 4](#)).
- **Baseline stroke risk:** This will be assessed during 12-month pre-index period using two alternative risk score schemes:
 - (1) the CHADS₂ stroke risk score is calculated by adding 1 point each for congestive heart failure, hypertension, diabetes, and age >75 years and 2 points for prior stroke or TIA (See [Appendix A, Table 5](#));
 - (2) the CHA₂DS₂-VASc stroke risk score - calculated by adding 1 point each for congestive heart failure/left ventricle dysfunction, hypertension, diabetes, vascular disease (prior myocardial infarction (MI), peripheral artery disease, or aortic plaque), age between 65-74, female gender, and 2 points for and age >75 years prior stroke or TIA (See [Appendix A, Table 6](#)).
- **Baseline bleeding risk:** This will be assessed during the pre-index period using the bleeding score of modified HAS-BLED (See [Appendix A, Table 7](#)).
- **Index exposure:** NOAC on the index date
- **Time to index exposure:** The time period in days between the first AF diagnosis observed in the pre-index period and the index date
- **Newly vs. Previously AF diagnosed:** patients with a claim for AF <3 months before the index date will be classified as newly diagnosed. Patients with a claim >3 months before the index date will be classified as previously diagnosed.
- **Duration of follow-up period:** The time period in days between the index date and the end of follow-up.

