Calcium channel blockers		3400000710, 3400000310, 3400001010, 3400001011, 3400001012, 3400001015, 3400001050, 3400001300, 3400001500, 3400001810, 3400001812, 3400001814, 3400002000, 3400002200, 3400002400, 3400003010
Verapamil	34000030100	3400003010
Diltiazem	340000101	3400001010, 3400001011, 3400001012, 3400001015, 3400001050
Digoxin/digitoxin	321000	3120001000
Dronedarone	35400028100320	3540002810
Amiodarone	3540000500	3540000500
Rhythm control medications		
Disopyramide (Norpace)	35100010	3510001010
Procainamide	3510002010	3510002010

Flecainide	3530001	3530001010
Propafenone	3530005	3530005000
Betapace (Sotalol)	33100045	3310004510, 3310004512
Tikosyn (Dofetilide)	35400025	3540002500
Quinidine	351000301	3510003010, 3510003030
Mexiletine	352000251	not exist
Moricizine	35050301003	not exist
Other		
ACE Inhibitors	3610	36100005, 36100010, 36100020, 36100025, 36100027, 36100030, 36100033, 36100035, 36100040, 36100050, 36100060
Angiotensin-II Receptor Blockers (ARB)	3615	3615004020, 3615003000, 3615002010, 3615008000, 3615005520, 3615007000, 3615002420, 3615001020
Diuretics (Thiazide, loop)	3720, 3760	3710001000, 3710001010, 3710002000, 3710003000, 3720001000, 3720002000, 3720002010, 3720003000, 3720008000, 3740001000, 3740003000, 3750001010, 3750002000, 3750003000, 3760001000, 3760002000, 3760002010, 3760002500, 3760004000, 3760005000, 3760005500, 3760006000, 3790003000, 3799000210, 3799000220, 3799000230, 3799200410
Antihypertensives (excluding above group)	3620, 3625, 3630, 3640, 3660	3610000510, 3610001000, 3610002010, 3610002510, 3610002710, 3610003000, 3610003310, 3610003510, 3610004010, 3610005000, 3610006000, 3615001020, 3615002010, 3615002420, 3615003000, 3615004020, 3615005520, 3615007000, 3615008000, 3617001010, 3620101010, 3620102510, 3620103000, 3620103010, 3620200510, 3620203010, 3620204010, 3620304000, 3625003000, 3630001010, 3630002010, 3630002500, 3640001010, 3640002000, 3640004010, 3640203010, 3660002010, 3699150220, 3699150223, 3699150270, 3699180215, 3699180225, 3699180235, 3699180240, 3699180255, 3699180260, 3699180265, 3699200210, 3699200213, 3699200220, 3699200230, 3699200240, 3699270250, 3699300205, 3699300210, 3699300270, 3699400210, 3699400220, 3699400225, 3699400230, 3699400245, 3699400250, 3699400260, 3699400270, 3699450320, 3699450345, 3699500220, 3699500270, 3699600215, 3699670210, 3699680320, 3699850250, 3699880260

Fondaparinux	83103030	8310303010 (Also include HCPCS code: Injection, fondaparinux sodium, 0.5 mg - J1652)

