Anticoagulants		
Dabigatran	833370302001	8333703020
Argatroban	83337015	8333701500, 8333701520
Warfarin	83200030	8320003020
Heparin	83100020	8310002020, 8310002022, 8310002025, 8310002030, (Also include HCPCS code: Injection, heparin sodium, (heparin lock flush), per 10 units - J1642 , Injection, heparin sodium, per 1000 units - J1644)
Enoxaparin	83101020	8310102010 (Also include HCPCS code: Injection, enoxaparin sodium, 10 mg - J1650)
Tinzaparin	83101080	not exist in GPI database (Include HCPCS code: Injection, tinzaparin sodium, 1000 iu - J1655)
Dalteparin	83101010	8310101010 (Also include HCPCS code: Injection, dalteparin sodium, per 2500 iu - J1645)
Rivaroxaban	83370060	8337006000
Apixaban	83370010	8337001000
Antiplatelet		
Clopidogrel	85158020	8515802010
Brilinta (ticagrelor)	85158470	8515847000
Prasugrel	85158060100330, 85158060100320	8515806010
Ticlopidine	85158080100320	8515808010
Cilostazol	85155516000320, 85155516000330	8515551600
Dipyridamole	85150030000310, 85150030000320, 85150030000330	8515003000
NSAIDs	6610	6610007000, 6610003000, 6610002000, 6610004010, 6610001010, 6610006000, 6610008000, 6610006010, 6610009010, 6610001200, 6610005000, 6610006500, 6610003500, 6610000710, 6610101000, 6610000720, 6610000800, 6610003710, 6610990220, 6610052500, 6610005200, 6610005500, 6610003010, 6610002040, 6610006050, 6610002050, 6610990328, 6610990244, 6610005260, 6610990232, 6610000700, 6610990241, 6610990340, 6610990435, 6610990337, 6610990217, 6610990338, 6610990256, 6610990440, 6610990339, 6610990315, 6610990317,

		6610990238,
--	--	-------------

Table 9. Outcome Codes

Medical Conditions	ICD-9 Codes	Description	ICD-10 Codes
Stroke		Inclusive of ischemic stroke and hemorrhagic stroke below	
Major Bleeding		Inclusive of hemorrhagic stroke, major intracranial bleeding and major extracranial bleeding below	
Ischemic Stroke (Primary Only)	433.x1	Occlusion and stenosis of precerebral arteries with cerebral infarction	I63.xxx
	434.x1	Occlusion of cerebral arteries with cerebral infarction	
	436	Acute, but ill-defined, cerebrovascular disease	I67.89
	Exclusion	EXCLUDE above codes if hospitalization lasted <48 hours and was accompanied by carotid endarterectomy (ICD-9 procedure code 38.1)	
Hemorrhagic Stroke (Primary Only)			
	431	Intracerebral hemorrhage (ICH)	I61.x

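### The HAS-BLED stroke row in Appendix A, Table 7 disagrees with the plan's own stroke and hypertension code lists, and its hypertension drug line has no stated rule

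*Combined protocol and SAP*

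**What the plan says.** Section 9.3.3 measures baseline bleeding risk with a modified HAS-BLED score defined in Appendix A, Table 7. Section 9.7 lists that score among the characteristics to be considered for the propensity model, and section 9.7.1 uses HAS-BLED to report bleeding risk. The only modification explained is the Table 7 footnote: labile INR is unavailable, so the maximum is 8. Scores of 0-1 are Low, 2 is Intermediate, and 3 or more is High.

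**Stroke row of Table 7.** In ICD-9 it takes 433.xx through 437.xx. In ICD-10 it takes "G45.x, G46.x, I63.xxx-I66.9, I67.1, I67.2, I67.4-I67.82, I67.84x-I68.8". Tables 2, 5, 6 and 9 restrict 433 and 434 to the x1 codes. Table 9 describes 433.x1 as "Occlusion and stenosis of precerebral arteries with cerebral infarction" and pairs the x1 codes with I63.xxx. In Tables 5 and 6 the ICD-9 hypertension list is "401.x-405.x, 437.2", with I67.4 on the ICD-10 side, and the Stroke/TIA item includes 438.x and I69.xxx.

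**Hypertension row of Table 7.** It gives diagnosis codes 401.x-405.x / I10-I16.x and then, with no connector, "Drugs used to treat hypertension (GPI codes 3300, 3400, 3610, 3615, 3620, 3625, 3630, 3640, 3660, 3720, 3760". Tables 2, 5 and 6 define hypertension by diagnosis only. Table 8 lists beta blockers and calcium channel blockers, with verapamil and diltiazem, under "Rate control medications".

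**The concern.** One code should not mean two conditions, or count as stroke in one score and not in another, when all the scores describe the same patients and are candidates for the same propensity model. As written, an occlusion code without the infarction digit earns a stroke point only in HAS-BLED. One code that is hypertension for CHADS₂ is stroke for HAS-BLED. A patient whose only record is a stroke sequela has had a stroke for CHADS₂ but not for HAS-BLED.

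The drug line raises a separate difficulty. Every patient in the cohort has AF, so a drug the plan itself lists for rate control is weak evidence of hypertension, and the plan does not say how a fill and a diagnosis combine.

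Major bleeding is a primary outcome, and HAS-BLED is the bleeding-risk measure that readers will use to judge whether the matched groups are comparable. If its items do not measure what their labels say, the reported classes and any balance check on the score lose meaning.

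**Working it through.** **The plan's own figure.** Table 7 points: hypertension 1, renal and liver 2, stroke 1, bleeding 1, labile INR 1, elderly 1, drug and alcohol 2. Total 9; without labile INR, 9 − 1 = 8. The stated maximum reproduces and does not change with the fix.

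**Stroke row, ICD-9 lists side by side.**

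| Code | Table 7 stroke | Tables 5/6 Stroke/TIA | Table 2 ischemic stroke |
|---|---|---|---|
| 433.11, 434.91 | yes | yes | yes |
| 433.10, 434.90 | yes | no | no |
| 435.9 | yes | yes | no (separate TIA row) |
| 436 | yes | yes | yes |
| 437.1, 437.9 | yes | yes | no |
| 437.0, 437.3 | yes | no | no |
| 437.2 | yes | no (hypertension row) | no |
| 438.9 | no | yes | no |
| 430, 431, 432.9 | no (bleeding row) | no | no |

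The ICD-10 side shows the same pattern. I65-I66 lie in the Table 7 range but outside I63.xxx and outside the Tables 5/6 item. I67.4 is stroke in Table 7 and hypertension in Tables 5/6. I69.xxx is in Tables 5/6 only. For TIA, Table 7 takes all of G45 and G46, while Tables 5/6 take a narrower set.

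**Hypertension row, prefix match.** The diltiazem codes are "3400001010, 3400001011, 3400001012, 3400001015, 3400001050"; all five, and the verapamil code 3400003010, begin with 3400 and match Table 7. The only beta-blocker GPI-10 codes listed are "3310004510, 3310004512". They begin with 3310, so the literal prefix 3300 misses them. Table 8 also lists the same two codes as sotalol under rhythm control. Table 3 uses the wider prefix 33.

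**Effect on the class.** All examples are patients over 65 (1 point) with no other qualifying codes.
- NSAID fill and 433.10: Table 7 gives 1 + 1 + 1 = 3, High. The Tables 5/6 stroke list gives 1 + 1 + 0 = 2, Intermediate.
- NSAID fill and 438.9: Table 7 gives 1 + 1 + 0 = 2, Intermediate. The Tables 5/6 list gives 1 + 1 + 1 = 3, High.
- A 401.x code and 437.2: Table 7 gives 1 + 1 + 1 = 3, High. With 437.2 not counted as stroke, 1 + 1 = 2, Intermediate.
- Diltiazem without a hypertension diagnosis, and 433.10: if the drug line stands alone, Table 7 gives 1 + 1 + 1 = 3, High. If a diagnosis is needed and the stroke row is aligned, the score is 1, Low.

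**Mean shift.** Let q be the share scoring the stroke point only through the extra Table 7 codes, r the share qualifying only through 438.x/I69.xxx, and p the share scoring hypertension from a drug alone. Aligning the stroke row changes the mean by r − q; also requiring a diagnosis subtracts p. The documents give none of these shares. For illustration only:
- p = 0.05, q = 0, r = 0: −0.05.
- p = 0.20, q = 0.05, r = 0: −0.25.
- p = 0.50, q = 0.20, r = 0: −0.70.
- p = 0, q = 0, r = 0.05: +0.05.

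The sign depends on the inputs.

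**The case against.** The score is declared modified, so it may depart from the other tables. Table 4 also uses a broad cerebrovascular range (430.x-438.x). Calcium channel blockers and beta blockers treat hypertension, and section 9.3.3 says so in effect: after listing them with diuretics it continues with "Other antihypertensives (i.e., angiotensin-converting-enzyme (ACE) inhibitors, combinations". Using fills to find hypertension that was never coded is a legitimate choice. TIA is scored in Tables 5 and 6 too. The rule is the same in every treatment group. Hypertension, ischemic stroke, TIA and the drug classes are separate candidates for the propensity model, and residual imbalance is to be adjusted for. No visible outcome analysis uses the Low/Intermediate/High classes.

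Most of this stands. The drug line does not contradict the other tables; it is non-specific in an AF cohort and lacks a rule. TIA in the stroke row is a choice to declare, not an error. The objection does not rescue the stroke row. The stated modification covers only labile INR, and Table 4 labels its range cerebrovascular disease, not stroke.

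Three stronger readings are tempting.
- *Rate-control drugs alone earn the hypertension point.* That is the likelier reading, because other Table 7 rows list diagnoses, procedures or drugs as alternatives, but no rule is written.
- *The score is inflated in a tenth to a quarter of patients.* Suppose 20% have no hypertension diagnosis, 25% take a calcium channel blocker, 70% take either rate-control class, and 5-10% carry a stroke-row code without infarction. Then 0.20 × 0.25 = 5% and 0.20 × 0.70 = 14%. Simple addition gives 5 + 5 = 10% to 14 + 10 = 24%; independence gives an upper end of 1 − 0.86 × 0.90 = 22.6%. Every input is assumed. The drug shares treat all patients without a diagnosis as free of hypertension, the 14% needs prefix 3300 to catch beta blockers, TIA is counted as false, and the omission of 438.x/I69.xxx is ignored.
- *The treatment comparison is biased.* Nothing in the documents shows that these errors differ between groups after matching.

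**Conclusion.** The stroke row of Table 7 is inconsistent with the plan's own definitions in three ways:
- It admits 433.x0/434.x0 and I65-I66.
- It counts 437.2/I67.4 as stroke.
- It omits 438.x/I69.xxx.

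For patients whose stroke point turns on these codes, HAS-BLED is off by one point, which changes the class at the boundaries 1 to 2 and 2 to 3. The errors run in both directions, so the score cannot be called inflated overall. The hypertension row is underspecified and non-specific rather than contradicted. What is shown is misclassification of one candidate covariate and one reported baseline measure. Severity is minor. The conclusion rests only on comparing the plan's code lists and needs no assumed prevalence.

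**What to change.** - **Stroke row.** Align Table 7 with the Tables 5/6 list: 433.x1, 434.x1, 436, 437.1x, 437.9x and 438.x, with I63.xxx, I67.8xx, I67.9 and I69.xxx. Remove 433.x0, 434.x0, 437.2, I65-I66 and I67.4, and the other codes that Tables 5/6 do not count (such as 437.0 and 437.3), or justify each one kept. I67.8xx retains I67.89, the ICD-10 partner of 436 in Tables 2 and 9. It would also bring in I67.83, which Table 7 skips and Table 4 excludes, so settle that code.
- **437.2/I67.4.** State whether it moves to the Table 7 hypertension row, as in Tables 5 and 6, or is dropped from the score.
- **Hemorrhage codes.** Leave 430.x-432.x / I60-I62 in the bleeding row only; adding them to stroke would score one event twice.
- **TIA.** Decide whether 435.x with G45/G46 scores, and treat both code systems alike.
- **Hypertension row.** State whether the drug line is an alternative to a diagnosis or needs one, and acknowledge that the 3400 drugs are non-specific here. Requiring a diagnosis loses patients known only from fills; their drug classes remain separate candidate covariates. Reconcile prefix 3300 with the listed 3310 codes.
- **Timing.** Re-derive HAS-BLED before the propensity model is fitted.

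Cost: a code-list edit and one re-derived variable.
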